This will be a prospective, single-arm single institution study with enrollment at the Texas Sinus Institute at The University of Texas Health Science Center at Houston. The patients will be enrolled through a 12-month time frame. Each patient will have a required 14-week participation window with an optional visit at 28 weeks as well. We will be assessing the objective and subjective response of RFA of the PNN in patients with rhinitis. At each post-procedure visit including the procedure visit, we will be assessing side effects and adverse events of the treatment. The primary outcome of this project is to determine how RFA of the PNN affects underlying cytokine profiles in addition to peak nasal inspiratory flow levels, which will be determined at weeks 0 and 12 for cytokine changes and weeks 0, 4, 12 and an optional 26 weeks for PNIF. The secondary outcomes of this study will be to assess how RFA of the PNN changes subjective symptom scores such as rTNSS and NOSE and this will be assessed at weeks 0, 4, 12 and an optional 26 weeks.

Study Population

Patients between the ages of 18-80 will be eligible for intervention if they have chronic rhinitis symptoms for at least 6 months (rhinorrhea, congestion, post-nasal drip), poor response to

medical management that was attempted for at least 4 weeks, a rTNSS score ≥ 6 , as well as ≥ 2 for rhinorrhea, and ≥ 1 for congestion. Exclusion criteria consists of active sinusitis, rhinitis medicamentosa, recurrent and ongoing epistaxis, immunodeficiency as defined by an illness or a history of sinus surgery. We will perform a query within the electronic medical record to assist in finding patients with chronic rhinitis.

The following ICD-10 codes will be used:

- J30.9 Allergic Rhinitis
- J30 Vasomotor rhinitis
- R09.82 Post-nasal drip/Chronic Rhinitis
- J34.89 Rhinorrhea
- J30.81 Animal Dander rhinitis
- J30.89 Dust rhinitis
- J30.5 Food induced rhinitis
- J31 Atrophic rhinitis

Then we will reach out to them and offer them participation in the study.

Study Procedures

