There will be a total of four required visits with an optional fifth visit. At the first visit, enrolled participants will be screened and stopped on all intranasal corticosteroids. The total clinic appointment should not exceed 30 minutes. At this visit, we will be obtaining all relevant demographic information for analysis such as age, gender, years of rhinitis symptoms, medical co-morbidities, types of medical management that had been trialed and for how long, history of other allergic symptoms, and specific allergic triggers or prior allergy test results. We will collect this through the electronic medical record and then collate and save this data on an encrypted hard drive. At the second visit (at least two weeks from the first visit), we will teach and train participants to perform PNIF for which we will take the highest of three repeated values, we will also collect rTNSS and NOSE values in addition to nasal secretions prior to the procedure. The patient will fill the symptom score evaluations out on handouts, and we will tabulate the responses on an encrypted drive. We will collect the PNIF values on the electronic medical record and then record and save them on an encrypted hard drive. Our laboratory has established a protocol utilizing a White Blood Cell Isolation Medium called Leukosorb (Pall Corporation, New York) for nasal secretions. The Leukosorb paper is an efficient way to collect nasal secretions for cytokine analysis. The 1 x 1 cm paper will be placed over the posterior aspect of the inferior turbinate near the treatment site under endoscopic visualization. The paper is left in place for 5 minutes and then retrieved into an Eppendorf tube on ice. The paper will be stored at -80 until processed. To process, the paper collected secretions are eluted from the Leukosorb paper by centrifugation and stored at -20C for analysis by Biolegend. For confidentiality, each patient will be assigned a study identification number and all samples collected will be labeled with a study identification number. The document key correlating patient to their study identification number will be stored in a password protected document on UT server. For the treatments, we will be using Neurent Medical's Neuromark™ system

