(Neurent, Ireland). This device has been approved by the FDA for treatment of chronic rhinitis. The NEUROMARK device is an in-office, disposable bipolar RFA device with a treatment tip consisting of micro electrodes which delivers RF energy while monitoring appropriate tissue contact to maximize delivery to posterior nasal nerve and its variable branching. After topical anesthesia consisting of oxymetazoline and 1% lido followed by 4% lidocaine, the device will be placed in the posterior inferior turbinate under endoscopic visualization. The device will be activated per manufacturer's instructions. After the procedure we will allow the patient to recover appropriately and ask for any adverse events or side effects at that time. We will detail these adverse events in the electronic medical record and record them in the encrypted hard drive. The second visit should take around 45-90 minutes. There will be subsequent visits at week four post procedure and week twelve post procedure. At week four we will be assessing side effects and adverse events in addition to obtaining rTNSS, NOSE, and PNIF values. This visit should not take more than 20-30 minutes. At week 12 post-procedure we will be obtaining rTNSS, NOSE, PNIF and nasal secretions for cytokine analysis. This visit should take around 30-45 minutes at most. The last optional visit, week 26 post-procedure, will be identical to week 4's visit, and should last no more than 30 minutes. The total clinic time required will be 150 minutes with an optional extra 30 (180 minutes) should patients want to participate in the final clinic visit. After week 12, statistical analysis and comparative analytics will be initiated.

Data and Safety Monitoring

Adverse events are not expected however should they occur patients will report them to the PI of the study. Any Adverse or unanticipated events will be reviewed monthly during regularly monthly meeting involving Drs. [name], [name] and [name]. The adverse events will be adjudicated by the committee. A log of these events will be kept. Any adverse event resulting from the device will be reported to the company.

Statistics

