This study will be a prospective analysis. The primary endpoint is the change in PNIF from baseline after RFN treatment of the PNN at 12 weeks. Prior literature has shown that treatment of rhinitis can lead to an increase of PNIF in variable amounts depending on baseline. Literature suggests an average increase of PNIF to be around 25-35 L/min after treatment, with a standard deviation (SD) of approximately 30 L/min. With an average expected change of 30, SD of 30, and 80% power at alpha of 0.05, the minimum sample size should be 32. Assuming a 10% dropout rate, we seek to enroll 36 eligible subjects. We will also perform analyses of rTNSS and NOSE scores. As has been published, a patient will be considered a "responder" if they have at least 30% reduction of rTNSS at 12 weeks and ≥ 1 NOSE class improvement or a reduction in NOSE at least 20% from pre-treatment. Additionally, the minimum clinically important difference (MCID) for the RQLQ(S) is established at ≥ 0.5 points and 20 for PNIF. We will be performing statistical analysis after each post-procedure visit, but the primary objective will be evaluation of the PNIF and cytokine changes after week 12. However we will also assess how PNIF scores change at weeks 4 and 26 in addition to week 12. The secondary outcomes will be to assess how RFA of the PNN changes subjective symptom scores such as rTNSS and NOSE at weeks 4, 12,

and 26. Comparative analytics will be performed on all groups. Paired t-tests, Wilcoxon-Mann t-tests, chi-squared tests and ANOVA analysis will be used. Criteria for termination of the study could be poor recruitment in which the study could not be completed within 3 years.

Ethics

We will be obtaining a waiver of consent for every patient. Each patient will have a unique identifier without any identifiable medical information. There is a risk of data breach however all information will be stored on a HIPPA compliant database on a University of Texas server that will be de-identified. The patient information will be kept using a linking log and a unique patient identifier for each patient. All data will be saved on encrypted University of Texas computers using the HIPPA compliant database. Patient information and data will be stored for three years.

Data handling and record keeping

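### Week 26 is an optional visit but a listed analysis time point, and the plan does not say how non-attendance will be handled

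*Combined protocol and SAP*

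**What the plan says.** Study Procedures sets the schedule: "There will be a total of four required visits with an optional fifth visit". The fifth visit takes place "should patients want to participate in the final clinic visit", so attendance is the patient's decision. Its content matches week 4: adverse events, rTNSS, NOSE and PNIF.

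Study Design is open about this. PNIF is measured at "weeks 0, 4, 12 and an optional 26 weeks for PNIF", and of the symptom scores it says "this will be assessed at weeks 0, 4, 12 and an optional 26 weeks".

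The Statistics section places the primary endpoint, the change in PNIF, at week 12, which is a required visit. It then adds "we will also assess how PNIF scores change at weeks 4 and 26 in addition to week 12", and lists weeks 4, 12 and 26 for rTNSS and NOSE as secondary outcomes. The word optional does not appear there. The tests named are paired t-tests, Wilcoxon, chi-squared and ANOVA, none of them assigned to an endpoint or visit. The section gives no analysis population, no missing-data method and no caveat for week 26. The only allowance for loss is 10% dropout in the sample size, which is built on the week-12 endpoint.

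**The concern.** A paired test uses only patients with both values. At week 26 these are the patients who chose to return, and that choice may well depend on how they are doing. Satisfied patients may come back, or patients whose symptoms have returned may. Either way, the attendee mean need not describe the treated group.

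Week 26 is the only planned measurement after week 12, so any statement about effect beyond 12 weeks rests on it. With a single arm, no control group shares the selection and could offset it. Two readings are at risk:

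- The week-12 mean of all patients set beside the week-26 mean of attendees. The difference contains selection as well as change over time.
- A repeated-measures ANOVA over weeks 0, 4, 12 and 26 restricted to complete cases. This would cut weeks 4 and 12 down to attendees too. The plan's unassigned ANOVA does not rule it out.

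**Working it through.** **The plan's own figures.** It gives none for week-26 attendance. Its dropout step reproduces: 32 / 0.90 = 35.6, rounded up to 36. That step concerns week 12.

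**Inputs.** From the Statistics section: SD of PNIF change 30 L/min, expected change 30 L/min, and MCID 20 (unit not stated; taken as L/min). Assumed, because the documents give no value: the same SD at weeks 12 and 26, a correlation ρ = 0.7 between the two changes, an attendance fraction p, and a correlation r = 0.3 to 0.5 between the propensity to attend and the change in PNIF (normal liability model).

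**1. Attendance depends on the week-12 change.** Bias of the attendee week-26 mean = r × ρ × SD × λ, where λ = φ(c)/p, φ is the normal density and c is the cut-point that gives attendance p. The product ρ × SD is 0.7 × 30 = 21.

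| Attendance | λ | r = 0.3 | r = 0.5 |
|---|---|---|---|
| 50% | 0.798 | 0.3 × 21 × 0.798 = 5.0 | 0.5 × 21 × 0.798 = 8.4 |
| 80% | 0.350 | 0.3 × 21 × 0.350 = 2.2 | 0.5 × 21 × 0.350 = 3.7 |
| 90% | 0.195 | 0.3 × 21 × 0.195 = 1.2 | 0.5 × 21 × 0.195 = 2.0 |

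At 50% attendance this is 5.0/20 = 25% to 8.4/20 = 42% of the MCID. A model that uses the week-12 data brings the bias to about zero, but only because attendance was made to depend on week 12 alone.

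**2. Paired week-12 to week-26 change within attendees, same scenario.** Bias = r × (ρ − 1) × SD × λ. At 50% attendance: 0.3 × (−0.3) × 30 × 0.798 = −2.2 and 0.5 × (−0.3) × 30 × 0.798 = −3.6 L/min. This is smaller than the bias in step 1 and of opposite sign: the paired trend exaggerates loss of effect, while the unpaired contrast hides it.

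**3. Complete-case ANOVA, same scenario.** The week-12 mean among attendees is off by r × SD × λ: 0.3 × 30 × 0.798 = 7.2 and 0.5 × 30 × 0.798 = 12.0 L/min at 50% attendance.

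**4. Attendance depends on the week-26 change itself.** The attendee week-26 mean is off by the same product, 7.2 to 12.0 L/min at 50% attendance. Simulation shows that adjusting for week 12 leaves about 3.8 to 6.6. So 3.8/7.2 = 53% to 6.6/12.0 = 55% remains.

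**5. A second route.** Bias = (1 − attendance) × (attendee minus non-attendee mean change). With 32 patients and 16 attending, assumed differences of 10, 20 and 30 L/min give biases of 5, 10 and 15. If the true mean change in all 32 were zero, a nominal 5% paired t-test (SD 30) would reject about 10%, 24% and 47% of the time. For a difference of 20, the rate is about 15% at 70% attendance and 6% at 90%.

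**6. Precision.** Power is not the main problem. For a change of 30 with SD 30, 10 pairs give 80% power and 16 pairs give 96%. The 95% interval half-width is 16.0 L/min with 16 attendees, against 10.8 with all 32.

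**The case against.** The strongest reply is that week 26 is disclosed as optional in Study Design and Study Procedures, is not the primary time point, and was never presented as complete follow-up. This stands. A reader of the Statistics section alone might infer that week 26 is an ordinary required time point, but the protocol as a whole does not support that. The gap is in the analysis, not in disclosure.

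A reader might also infer that a paired test of week 12 against week 26 mixes two different sets of patients. It does not: it uses the same patients at both times, and attendees are a subset of those seen at week 12. The mixing arises only when the all-patient week-12 mean is compared with the attendee week-26 mean. The paired trend is still selected, but by the smaller amount in step 2.

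Nor do the documents assign paired tests to week 26; that use is inferred from a general list. The inference is reasonable, because nothing else is offered for a within-patient change.

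The sizes rest on assumed attendance and correlations, and the direction is unknown. Every bias in step 1 is below the MCID of 20 and the expected change of 30, and at 50% attendance it is also below the interval half-width of 16.0. If nearly everyone returns, little is at stake. All of this is correct and limits the weight of the point. It does not remove it, because the plan has no provision if attendance turns out to be low.

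**Conclusion.** The concern holds in limited form. Followed as written, the plan gives week-26 estimates for self-selected attendees, with nothing to show how they differ from the rest. Under the stated assumptions, with selection on the week-12 change, the attendee mean is off by about 5 to 8 L/min at 50% attendance, 2 to 4 at 80% and 1 to 2 at 90%. The within-attendee trend is off by about 2 to 4 at 50%. These are scenarios, not estimates, and the sign could be either.

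The week-12 primary endpoint comes from a required visit and is not touched, except by a complete-case repeated-measures ANOVA over all visits. It would be wrong to infer that the primary result is compromised. The point should be settled before analysis because a better method is available at little cost.

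**What to change.** In the Statistics section:

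1. Estimate the week-26 means, and the change from week 12 to week 26, from a mixed model for repeated measures using weeks 0, 4, 12 and 26 in all treated patients, for PNIF, rTNSS and NOSE. State that complete-case repeated-measures ANOVA over all visits will not be used.
2. Report the number attending week 26, and tabulate week-0 and week-12 values for attendees and non-attendees.
3. Label week-26 results exploratory.

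The cost is a few sentences, one model and one table, with no new data. The downside is that the model relies on data missing at random. If attendance depends on the week-26 state itself, about half the bias remains, so the attendance table should be read with the estimate.

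Sending the symptom questionnaires to patients who decline the visit is not recommended. It would mean contact after their required participation has ended, change the mode of collection, and do nothing for PNIF.

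### The listed tests are not tied to endpoints, and in this single-arm before/after trial the rank test reads as unpaired and the ANOVA is not called repeated-measures

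*Combined protocol and SAP*

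**What the plan says.** The Study Design section states: "This will be a prospective, single-arm single institution study". It schedules measurements at "weeks 0 and 12 for cytokine changes and weeks 0, 4, 12 and an optional 26 weeks for PNIF", with rTNSS and NOSE on the same visits as PNIF. Each efficacy outcome is therefore a change within the same patients.

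The Statistics section names week-12 change in PNIF as the primary endpoint, then says "the primary objective will be evaluation of the PNIF and cytokine changes after week 12". The Study Design section likewise says that the "primary outcome of this project is to determine how RFA of the PNN affects underlying cytokine profiles" together with PNIF.

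The methods are given in two consecutive sentences of the Statistics section: "Comparative analytics will be performed on all groups" and "Paired t-tests, Wilcoxon-Mann t-tests, chi-squared tests and ANOVA analysis will be used". The groups are not defined, and no method is linked to any endpoint. The signed-rank test, repeated-measures ANOVA and mixed models are not mentioned anywhere.

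**The concern.** Of the four methods listed, only the paired t-test is clearly a within-patient method. Wilcoxon-Mann t-test is not a standard name. The nearest standard one is Wilcoxon-Mann-Whitney, which compares independent samples, although the signed-rank test may have been meant. ANOVA without qualification usually means the between-groups form.

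An analyst who treats visits as if they were different patients leaves the between-patient variation in the error term. When visits are positively correlated, the p-values are then too large. A modest real change in cytokines, symptom scores or multi-visit PNIF could be reported as no effect. Separately, a list with no assignment leaves the choice of test open until the data have been seen.

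**Working it through.** **Inputs.** From the Statistics section: 32 evaluable patients, change 30 L/min, SD 30 L/min, 80% power, alpha 0.05 (two-sided assumed), 10% dropout. The documents give no within-patient correlation r and no effect size for cytokines or symptom scores. I therefore assume r = 0.3, 0.5 and 0.7, normal data, and a range of shifts in units of the single-visit SD.

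**Step 1: the plan's own sample size.** For two independent groups, n per group = 2 × (1.96 + 0.84)² × (30/30)² = 15.7, so 16, or 32 in total. Then 32/0.9 = 35.6, so 36. Both stated figures are reproduced. The paired formula with SD of change 30 gives (1.96 + 0.84)² = 7.85, so 8, or 10 with the t distribution. The stated 32 therefore matches an independent-groups calculation. That does not show which tests will be run, but it means a paired reading of the test list cannot be taken for granted.

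**Step 2: why ignoring pairing costs power.** The unpaired variance of the mean difference is 2σ²/n. With correlation r the true variance is 2σ²(1 − r)/n.

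- Null rejection rate of an unpaired test: 2Φ(−1.96/√(1 − r)) = 1.9%, 0.6%, 0.03% for r = 0.3, 0.5, 0.7, instead of 5%.
- Unpaired z at a 0.5 SD shift: 0.5 × √(32/2) = 2.00. Power is Φ((2.00 − 1.96)/√(1 − r)) = 52/52/53%.
- Paired z: 2.00/√(1 − r) = 2.39, 2.83, 3.65. Power is Φ(z − 1.96) = 67/81/95%.

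These are normal approximations for tests on means. Rank tests run a few points lower.

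**Step 3: simulation of the actual tests** (n = 32, two-sided 0.05; triplets are r = 0.3/0.5/0.7; repeat runs agree to within one or two points).

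| Two visits, shift | Mann-Whitney | Signed-rank |
|---|---|---|
| 0 (type I error) | 2.1/0.8/0.1% | about 5% |
| 0.3 SD | 18/14/9% | 28/37/55% |
| 0.5 SD | about 48% at each r | 62/77/93% |
| 0.8 SD | 90/93/97% | 95/99/100% |
| 1.0 SD | 99–100% | 99–100% |

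| Weeks 0, 4, 12, shift at both later visits | One-way ANOVA | Repeated-measures ANOVA |
|---|---|---|
| 0.5 SD | 48/47/45% | 67/82/97% |
| 0.8 SD | 94/96/98% | 98/100/100% |

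**Step 4: what the listed paired t-test already covers.** On logged cytokine-like data with a 0.5 log-SD change, the paired t-test has 64/78/94% power, close to signed-rank. For week-12 PNIF, if 30 is the SD of the change, 32 patients give more than 99.9% power for a change of 30. If 30 is instead the SD of a single measurement, the planned change is 1.0 SD, where even the unpaired test has 99–100% at these correlations.

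**Step 5: the optional visit.** Classical repeated-measures ANOVA over four visits drops every patient without week 26. If half attend (an assumption) and the shift is 0.5 SD at all later visits, the 16 complete patients give 36/48/72% power. A within-patient model using all available visits gives 63/80/96%.

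**The case against.** The strongest reply is that the list makes sense as written. It directly follows a sentence about comparing groups, and rank-sum, chi-squared and ANOVA are ordinary tools for that. Possible groups are at hand: allergic against non-allergic rhinitis (Background Information), the diagnosis codes (Study Population), or responders, defined partly by "if they have at least 30% reduction of rTNSS at 12 weeks". On that reading the paired t-test handles change and the other methods handle groups. Nothing says that an unpaired test will be run on before/after data. All of this stands, and it makes the harm conditional. It does not remove the point, because the plan names no such comparison and the groups are left undefined.

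Second, the paired t-test is available for every two-visit contrast, so Mann-Whitney against signed-rank is not the only relevant comparison. This also stands: if the t-test is used on logged cytokine values, the loss disappears.

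Third, the correlations, shifts and week-26 attendance are all assumed. That is correct, and it is why ranges are shown.

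A reader might infer more than the documents support:

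- *That the week-12 PNIF primary will be analysed wrongly.* A suitable test for it is on the list.
- *That cytokines alone lack a test.* No endpoint has an assigned test.
- *That unpaired tests would inflate false positives.* With positive correlation they do the opposite. The separate risk of choosing among unassigned tests after seeing the data could inflate them. The documents do not say how the choice will be made, so this risk cannot be sized.

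**Conclusion.** The point holds in a limited form. The plan ties no method to an endpoint, its only named rank test reads as unpaired, and its ANOVA is not said to be repeated-measures. If those two methods were used on before/after data, power for a 0.5 SD shift would be roughly 45–48% where a paired method would give 62–97%, depending on method and correlation. For shifts of 0.8 SD or more the gap is at most about six points. These figures rest on 32 patients, normal data and assumed correlations of 0.3 to 0.7.

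The exposure is in cytokine change, rTNSS, NOSE and multi-visit PNIF. Cytokine change matters most, because it is part of the stated primary objective, has no power calculation of its own, and may call for a rank test if skewed. The correction is worth making, but the point does not threaten the validity of the PNIF primary.

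**What to change.** In the Statistics section, replace the general list with one method per endpoint, fixed before any outcome data are analysed:

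1. **Week-12 PNIF primary:** keep the paired t-test.
2. **Each cytokine, week 0 to 12:** replace the Wilcoxon-Mann entry with the Wilcoxon signed-rank test, or use the paired t-test on log values. State one choice for all cytokines.
3. **PNIF, rTNSS and NOSE across visits:** replace ANOVA with a mixed model for repeated measures using all available visits, because week 26 is optional.
4. **Mann-Whitney, chi-squared and between-group ANOVA:** restrict them to named patient subgroups (for example allergic against non-allergic), or delete them together with the sentence on groups.

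The cost is a few sentences of text and a little more analysis work. No patients, visits or measurements are added.

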Effects of Radiofrequency Ablation of Posterior Nasal Nerves on Inflammatory Cytokines, Peak Nasal Inspiratory Flow, and Nasal Blood Flow in Patients with Chronic Rhinitis

NCT05648565

Version Date: 1/19/2023

Protocol Title:	Effects of Radiofrequency Ablation of Posterior Nasal Nerves on Inflammatory Cytokines, Peak Nasal Inspiratory Flow, and Nasal Blood Flow in Patients with Chronic Rhinitis
Principal Investigator:	[name]
Co-Investigators:	[name], [name], [name], [name]
Study Coordinator:	[name]
Population:	Will be enrolling at least 36 patients of good health with chronic rhinitis. Patients will be eligible for intervention if they have chronic rhinitis symptoms for at least 6 months and have failed medical treatment. Patients will be enrolled at the Texas Medical Center in Houston, Texas.
Number of Sites:	Single site / UT Houston is the only site
Study Duration:	Twelve Months
Subject Duration:	14 weeks, 28 weeks if patients decide to participate in the optional last patient visit

General Information

Patients with chronic rhinitis (CR) often fail medical management. In-office radiofrequency ablation (RFA) of the posterior nasal nerve (PNN) has been established as an effective therapy for CR. However, understanding the objective response, such as nasal patency as determined by peak nasal inspiratory flow (PNIF) and changes to type 2 cytokine profiles, to this treatment has yet to be elucidated. We will be performing RFA of the PNN and evaluating the change in PNIF, patient symptom scores and cytokine changes thereafter in patients with CR.

Background Information

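### The Ethics section plans a waiver of consent for every patient and states no scope, which does not fit a prospective study that stops medication, samples secretions and performs ablation

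*Combined protocol and SAP*

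**What the plan says.** The Ethics section opens with the sentence "We will be obtaining a waiver of consent for every patient". It does not say what the waiver covers, at which stage it applies, or why it is sought. The rest of that section deals with identifiers, secure storage, retention and the risk of a data breach.

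Other sections describe what happens to the same patients:

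- General Information: "We will be performing RFA of the PNN and evaluating the change in PNIF, patient symptom scores and cytokine changes thereafter".
- Study Population, after the query of the electronic record: "Then we will reach out to them and offer them participation in the study".
- Protocol summary, Subject Duration: "28 weeks if patients decide to participate in the optional last patient visit".
- Study Procedures, first visit: "At the first visit, enrolled participants will be screened and stopped on all intranasal corticosteroids".
- Study Procedures, second visit: "we will also collect rTNSS and NOSE values in addition to nasal secretions prior to the procedure".
- Study Procedures, treatment, after topical anesthesia: "the device will be placed in the posterior inferior turbinate under endoscopic visualization".
- Study Design, timing of the cytokine samples: "weeks 0 and 12 for cytokine changes".

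**The concern.** A waiver of consent with no stated limit is wording one might expect in a records study. Here it stands in the protocol of a prospective interventional study whose staff speak to each patient in advance and whose patients choose whether to take part. Read as written, it extends to people whose existing treatment is changed for the study, who are sampled for research and who undergo ablation.

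What is at stake is participant protection. An ethics board or auditor working from this sentence could not tell which study actions the waiver is meant to reach. The statistical results are not at stake.

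**Working it through.** The plan gives no figure on this point and no arithmetic applies. The check is to read the sentence against the sections that describe the study's actions, and to ask whether anything narrows it.

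**1. Whom does the sentence reach?** It refers to every patient. The next sentence of the Ethics section gives each patient an identifier. Study Procedures likewise gives each patient a study number, which is used to label the samples. The people who are sampled and treated are therefore within the wording. Study Population also uses the word patients for candidates found by the record query, so a narrower group may have been in mind, but the sentence is not confined to it. The planned number is at least 36 in the protocol summary and 36 in the Statistics section.

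**2. What is done to them?**

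| Activity | Where described | Fit with an unrestricted waiver |
|---|---|---|
| Search of the electronic record by diagnosis code | Study Population | Could be what the waiver was meant for |
| Contact and offer of participation | Study Population | Poor: the patient is asked beforehand and may decline |
| Intranasal corticosteroids stopped | Study Procedures, first visit | Poor: a study-directed change to existing treatment |
| Nasal secretions collected for cytokine analysis | Study Procedures, second visit and week 12 | Poor: sampling for research |
| Radiofrequency ablation under topical anesthesia | Study Procedures, second visit | Poor: an intervention performed within the study |
| Optional visit at week 26 | Study Procedures; Subject Duration | Poor: attendance is the patient's decision |

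**3. Does anything narrow the sentence?** The text around it concerns only data, and the only risk named there is a data breach. That is compatible with a waiver for access to records, but the section does not say so. No other section of the available text limits the waiver to the record query, to screening or to documentation of consent.

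**4. Which readings are possible?** There are three: a waiver for the record query, a waiver of documentation of consent, or a full waiver. The first two would be workable if stated. The third does not fit the activities in the table. The wording does not separate them, and taken literally it gives the third.

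**The case against.** The strongest reply is that this is a question of unclear scope rather than a contradiction. No sentence says that consent will be obtained, so no two statements are directly opposed. An offer of participation and an optional visit show that patients choose; they do not describe a consent process. The context also favours a narrow meaning: candidates are found through the electronic record, background data at the first visit are taken from that record, and the rest of the Ethics section is about data. The device is described as FDA-approved for chronic rhinitis, so the ablation might be seen as ordinary care.

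Much of this stands. The intended meaning cannot be settled from the text, and a narrow one is plausible. It does not cure the sentence, because none of that context is written into it. Device approval does not turn the study-directed stop of corticosteroids or the cytokine sampling into routine care, and General Information presents the ablation as something the study performs.

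A reader might be tempted by three stronger inferences, none of which the documents support:

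- *That no consent form exists, or that patients were treated without consent.* Consent pages were removed from the text available for this review, so their absence shows nothing.
- *That the sentence must contradict any consent form.* A waiver limited to the record query would be compatible with a signed form. Only an unrestricted waiver would not be.
- *That the waiver is already in force.* The sentence is in the future tense and authorises nothing by itself.

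**Conclusion.** The concern holds as a defect of wording. The sentence states a waiver without limit, and an unrestricted waiver does not fit a prospective study with these procedures. It applies to all planned participants, at least 36. No endpoint, sample size or analysis changes.

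Confidence is high that the scope is unstated and that the literal reading is unsuitable. There is no basis for confidence about what the authors meant, and no finding is made on how consent was handled. The conclusion rests on the sentence as printed and on the activities described in the other sections, not on the absence of consent material. It should be corrected despite the lack of statistical effect, because it concerns participant protection and followed literally it would be wrong.

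**What to change.** Rewrite the Ethics sentence so that it:

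1. limits any waiver to the named activity it is meant for, for example the electronic-record query under Study Population, or documentation of consent if that was the intention;
2. states that each participant's informed consent is obtained before any study-directed action, including the corticosteroid stop, study measurements, secretion sampling and the procedure;
3. agrees with Study Population, Study Procedures and any consent form.

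The cost is protocol wording, the matching ethics-board wording, and possibly some time for consent, which the documents do not quantify. The design, visit schedule and analysis need no change.
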